## 7.0 Missing data

Missing data have the potential of decreasing the power of the study resulting in either under or over estimation of the effect of the confident care guideline of shoulder pain management. This means that missing data may potentially lead to biased estimates. For example, the bias in model estimates may be introduced if the missing data for the outcome measure, SPADI is related to the reason for the data missing. This may occur if, for some reasons more younger patients decide to withdraw from the study leaving older patients who are more likely to be at higher risk of shoulder pain.

Rubin first described three forms of missingness in the data based on the reasons for the missingness [ref]. The methods for handling data missingness in research depend on the missingness mechanism. The mechanisms are missing completely at random (MCAR), missing at random (MAR) and missing not at random (MNAR). MCAR describes a situation where the data missing are independent of the observed outcomes and the covariates. For example, if a patient

decides to attend a wedding instead of completing the questionnaire on health related quality of life. MNAR is missingness that is neither MCAR nor MAR. It occurs when data missingness is dependent on the unobserved data. For example, patients with chronic shoulder pain are less likely to report the number of sick leave days if they think that this may reveal the amount of support they are getting from NAV. However, a more practical assumption that we shall assume in this study, is MAR. This occurs when the missingness depends on the observed outcomes and possibly on the observed covariates. For example, data on SPADI may be missing if a patient is withdrawn from the study due to a suspected case of inflammatory joint disease.

To account for the fact that clustered data are dependent, we shall use multilevel multiple imputation using the **miceadds** package in R. The imputed data shall be saved and the data shall be analyzed using StataSE. However, we shall only consider multilevel MI if 10% or more of the data are missing.

## 8.0 Reporting of adverse events

We do not believe that there shall be adverse events associated with the implementation of the confident care nor adverse event related to the usual care. Therefore, no analysis and reporting of adverse events is planned.

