#### 4.1 Primary outcome

The primary outcome measure is the Shoulder Pain and Disability Index (SPADI), which is a self-reported questionnaire with 13 items regarding shoulder pain and disability. These are patient level observations obtained at time points 0, 1, 2 and 3 denoting baseline, 6 weeks, 12 weeks and 52 weeks respectively.

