## 4.2 Secondary outcome

Several secondary outcome measures, also at patient level, shall be obtained. These will be measured either on four different measurement scales: Likert, ordinal, categorical (binary measures) and as counts.

The outcomes that will be measured on a Likert scale are

- EQ5D-5L (Health related quality of life) with scores ranging from 0 to 1.00
- Orebro-10 with scores ranging from 0 to 100
- Fear avoidance belief questionnaire activity (FABQ-A) with scores ranging from 0 to 24
- Pain self-efficacy Questionnaire with scores ranging from 0 to 60
- Brief Illness Perception Questionnaire (B-IPQ) with scores ranging from 0 to 90
- Patient experience Questionnaire with scores ranging from 17 to 88

The following secondary outcomes will be measured on an ordinal scale

- Participant global improvement
- Participant satisfaction with treatment

The binary outcomes to be categorized into (0/1) for (No/ Yes) will include the following secondary outcomes

- Work
- Work disability (sick leave)
- Medication usage such as over the counter pain medications, corticosteroid injections

Two count variables that we will consider are

- The number of sick leave days
- Medication usage frequency

With the exception of participant global improvement and participant satisfaction with treatment, all secondary outcomes will have baseline measurements.

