All results from the mixed effects binary logistic regression models shall be presented as estimated odds ratios with 95% CIs. For both linear and binary/ ordered mixed effects regression models, estimates of intra-cluster correlation (ICC), which describes the amount of variability in the outcome measures that can be attributed to differences between the general practices and the GPs within the general practices shall be obtained from the models. However, results from the count regression models shall be presented as incidence rate ratios (IRR) with their 95% CIs. For example, the IRR shall represent the **changes** in the number of sick day leave at a certain time point relative to the referent group. IRR estimates that are significantly above 1 shall represent significant increases in the number of sick leave days whereas IRR estimates that are significantly less than 1 shall represent significant decreases in the number of sick leave days.

We shall use descriptive statistics to summarize categorical data in the form of frequencies (counts) and percentages. Normally distributed continuous variables shall be summarized using the mean and standard deviation (SD) whereas non-normal continuous data shall be summarized using medians with first and third quartiles.

All analyses shall be performed using StataSE statistical package and the significance level shall be set at  $\alpha = 0.05$ .

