### Statistical Analysis Plan (SAP)

The confident shoulder study

in clinics and  $\varepsilon_{ijk}$  is the random error assumed to be homogeneous and uncorrelated with mean 0 and variance  $\delta^2$ .

### Model 2

To assess if any potential effect of the intervention on SPADI is also related to time, we shall introduce a time component  $T$  in model 2 and explore how the impact of the intervention develops over time.

$$\text{SPADI}_{ijk} = \beta_0 + \beta_1 I_{ijk} + \beta_2 T_t + \alpha_{ijk} + \varepsilon_{tijk}$$

Here, the parameter estimate  $\beta_2$  represents the effect of time.

### Model 3

Model adjustment of patient level characteristics presented in section 5 above shall be considered in model 3 as follows:

$$\text{SPADI}_{ijk} = \beta_0 + \beta_1 I_{ijk} + \beta_2 T_t + [\beta]X_{ijk} + \alpha_{ijk} + \varepsilon_{tijk},$$

where  $[\beta]$  is a matrix of the patient level covariates. The covariates that we shall consider include the following: patient age, gender, marital status, years of education and occupational status. In addition, GP level covariates such as age, gender, years since graduation, specialty, type of practice, number of GPs in the practice, the number of weekly working hours, and number of people on the GPs' lists at recruitment shall be considered for model adjustment by introducing an additional term,  $[\beta_1]X_{ijk}$  if necessary.

### Model 4

We also believe that the intervention may either decrease SPADI score over time as the GPs gain experience and are confident with the intervention or SPADI scores may increase over time if, for example, the GPs become less enthusiastic about it or if the intervention is not effective. Therefore, we will consider a two-way interaction between time and exposure to the intervention in model 4.

$$\text{SPADI}_{ijk} = \beta_0 + \beta_1 I_{ijk} + \beta_2 T_t + [\beta]X_{ijk} + \beta_3 T_t I_{ijk} + \alpha_{ijk} + \varepsilon_{tijk},$$

The parameter estimate  $\beta_3$  is the interaction between time and exposure to the intervention  $I$  (1 = exposure and 0 = control).

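### Section 8.0 rules out all adverse event analysis and reporting on a belief that none will occur, so recorded events and the number of patients who get worse would go unreported

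*SAP*

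**What the plan says.** SAP section 8.0 consists of a belief and a conclusion. The belief is: "We do not believe that there shall be adverse events associated with the implementation of the confident care"; the same is said of usual care. The conclusion follows directly: "Therefore, no analysis and reporting of adverse events is planned". No data or reference is given.

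Other sections plan data and analyses that bear on worsening:

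- Section 4.1, on SPADI: "These are patient level observations obtained at time points 0, 1, 2 and 3 denoting baseline, 6 weeks, 12 weeks and 52 weeks respectively".
- Section 4.2 lists "Participant global improvement" as an ordinal outcome, sick leave as a binary outcome and sick leave days as a count. It also lists "Medication usage such as over the counter pain medications, corticosteroid injections" as a No/Yes outcome.
- Section 6.0 reads the count models in both directions: "IRR estimates that are significantly above 1 shall represent significant increases in the number of sick leave days".
- Section 6.1, Model 4, allows that "SPADI scores may increase over time if, for example, the GPs become less enthusiastic about it or if the intervention is not effective" and adds a time-by-intervention interaction for that reason.

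**The concern.** Absence of harm is assumed, and the assumption then becomes the ground for not looking. This is not a silence that the protocol might fill. It is an explicit rule about what will be analysed and reported. If an adverse event came to the trial team's notice under either condition, the SAP as written gives it no place in the results.

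The planned models do not replace this. They estimate mean differences, odds ratios and rate ratios between conditions. A favourable mean SPADI difference is compatible with some patients having deteriorated, and no planned summary counts them. A reader deciding whether to adopt the guideline would see average effects but neither the number who got worse nor any events. A later sentence saying that the guideline was safe, or that no harms were seen, would have nothing behind it.

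**Working it through.** The SAP gives no figure on this point, so there is none to reproduce. The check is a comparison of sections, followed by a rough measure of what reporting could show.

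**Step 1. What is covered without section 8.0, and what is not.**

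- *SPADI, average worsening:* covered by the linear mixed models of section 6.1. *Number of patients who worsened:* not planned anywhere.
- *Sick leave, sick leave days, medication use:* covered as group contrasts by the logistic and count models of sections 6.0 and 6.2.
- *Global improvement:* covered by ordered logistic regression (section 6.0). Section 6.0 also plans frequencies and percentages for categorical data, but does not say they will be split by condition.
- *Withdrawals by reason and condition:* not planned. Section 7.0 mentions withdrawal only when discussing missing data.
- *Adverse events that are reported:* excluded by section 8.0.

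The gap is therefore reported events, reasons for withdrawal, and counts of individual deterioration.

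**Step 2. What event reporting could show.**

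Inputs from SAP section 2.0: 250 patients to recruit and 10% dropout. The number 250 is taken as stated. Assumptions, not from the SAP: patients are independent, and they divide evenly between conditions. The SAP gives no split.

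- All recruited: 250. After dropout: 250 × 0.9 = 225.
- Per condition: 250 / 2 = 125, or 225 / 2 = 112.5, taken as 112.

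The one-sided 95% upper bound with zero events is 1 − 0.05^(1/n). The chance of seeing an event of true rate 1% at least once is 1 − 0.99^n.

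| n | upper bound, zero events | chance of seeing a 1% event |
|---|---|---|
| 250 | 1.2% | 0.92 |
| 225 | 1.3% | 0.90 |
| 125 | 2.4% | 0.72 |
| 112 | 2.6% | 0.68 |

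The larger n is the more natural one for events, because patients who drop out can also have them. An uneven split would weaken the bound in the smaller condition. These figures presuppose that events are recorded. Where they are not, or are not reported, no bound can be stated.

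**Step 3. Can deterioration be counted from planned data?**

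SPADI at baseline, 6, 12 and 52 weeks is enough for a count of patients who worsened. A threshold is needed, and the SAP has none for individuals: the 8 points in section 2.0 are a difference between groups, used for power. Condition also needs a definition. Section 3.1 classes observations by whether they fall before or after the practice's randomised crossover, and section 1.2 has every practice cross over by the end. A patient recruited under usual care can therefore reach 52 weeks after the practice has crossed.

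**The case against.** The strongest reply is that worsening is analysed already. Section 8.0 excludes adverse events; it does not exclude outcomes that move the wrong way. SPADI, sick leave, medication use and global improvement all have models, and section 6.0 says how an unfavourable rate ratio will be read. The objectives and hypotheses (sections 1.3 and 1.4) concern clinical outcomes, feasibility and health economics, and the SAP makes no safety claim. All of this stands, and it limits the point to reported events, withdrawals and individual counts.

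A reader might infer more than the SAP supports:

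- *That no harm of any kind would be seen.* Not so: average worsening remains visible in the models.
- *That the SAP expects harm and ignores it.* The remark in Model 4 concerns fading enthusiasm among GPs or an ineffective intervention, and the interaction is then modelled.
- *That withdrawals for suspected inflammatory joint disease are foreseen as a safety signal.* Section 7.0 uses this only as an illustration of data missing at random and does not link it to the guideline.
- *That the guideline changes injection or medication use.* The SAP does not describe the guideline's content. It only lists these as outcomes.

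It may also be said that the SAP does not show that withdrawal reasons or spontaneous events are recorded. That is right and may be settled in the protocol, so the fix asks for them only where recorded. None of this supports a rule that recorded events will not be reported because none were expected.

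**Conclusion.** The point holds in limited form. Section 8.0 turns an unsupported belief into a rule against reporting adverse events. Recorded events and the number of patients who deteriorate would go unreported, and the trial could not support any statement on the guideline's safety. The primary SPADI estimate is unaffected, and average worsening stays visible in the effectiveness models.

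The information forgone is modest: with no events seen, an upper bound of about 1.2% over all 250 patients, or about 2.4% to 2.6% in one condition. These figures rest on independent patients, complete recording and, for the per-condition values, an even split that the SAP does not give. The conclusion does not depend on them. This is a cheap improvement to reporting, not a threat to the primary result.

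**What to change.** Replace the last sentence of section 8.0 with a plan for descriptive reporting, without testing, by the condition assigned at the patient's recruitment under the randomised crossover schedule:

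1. any adverse events recorded;
2. withdrawals, with reasons where recorded;
3. the number and percentage of patients whose SPADI worsened from baseline at 6, 12 and 52 weeks, using a threshold fixed in advance and labelled as pragmatic. If 8 points is used, say that it is the SAP's between-group difference and not a validated individual threshold;
4. the number and percentage in any worse categories of global improvement, if the scale has them.

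Add three caveats: the trial is not powered for safety; crude comparisons between conditions are confounded with calendar time in a stepped wedge; and 52-week data of patients recruited under control may fall after their practice's crossover.

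The cost is one extra descriptive table that needs cautious interpretation. Items 3 and 4 use data already planned. Items 1 and 2 depend on what is recorded, which should be checked against the protocol.
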